14.3 DATA Safety Monitoring Board

This is a DSMP Level I study under the SKCCC Data Safety Monitoring Plan (12/6/2012). The Clinical Research Office will perform an audit after the first subject has been treated and then periodically depending on the rate of accrual and prior audit results. All trial monitoring and reporting will be reviewed annually by the SKCCC Safety Monitoring Committee. The PI is responsible for internally monitoring the study. Data must be reviewed to assure the validity of data, as well as, the safety of the subjects. The PI will also monitor the progress of the trial, review safety reports, and clinical trial efficacy endpoints and to confirm that the safety outcomes favor continuation of the study

15. STUDY ADMINISTRATION Trial Organization

This is a single center randomized clinical trial. The Steering Committee (SC) will act as the regulatory, policy, and decision-making body for the study. The SC will have complete oversight over study implementation, provide scientific decisions and advice, monitor protocol adherence, and provide overall management. For the initial part of the trial, the following subcommittees will work with the SC:

- Administrative Sub-Committee: in charge of protocol approval, update, and administrative matters.
- Recruitment Sub-Committee: in charge of developing recruitment strategies and monitoring recruitment progress.

- Metformin Sub-Committee: concerned with the scientific details and implementation of metformin intervention arm
- Coach-Directed Behavioral Weight Loss Sub-committee: concerned with the scientific details and implementation of life style modification arm.
- Data Management and Analysis Sub-committee: concerned with randomization, data management, data quality control, report(s) to DSMB, and statistical analysis.
- Clinician Review Committee: in charge of reviewing eligibility, adverse events, and safety.

Ethics and Good Clinical Practice

This study must and will be implemented according to protocol and Good Clinical Practice as described in:

- ICH Harmonized Tripartite Guidelines for Good Clinical Practice 1996.
- US 21 Code of Federal Regulations dealing with clinical studies (including parts 50 and 56 concerning informed consent and IRB regulations).
- Declaration of Helsinki, concerning medical research in humans (Recommendations Guiding Physicians in Biomedical Research Involving Human Subjects, Helsinki 1964, amended Tokyo 1975, Venice 1983, Hong Kong 1989, Somerset West 1996).

Funding Mechanism and Sponsors

This study is supported by the State of Maryland Cigarette Restitution Fund. The Johns Hopkins Kimmel Cancer Center is providing additional support.

16. SAMPLE SIZE

The trial has sufficient resources to enroll ~120 participants, who will be randomly allocated in equal proportions to each of 3 arms:

- Group A: Self-directed weight loss arm.
- Group B: Coach-Directed Behavioral weight loss intervention arm.
- Group C: Pharmacological intervention using metformin.

The primary contrasts are (C vs. A) and (B vs. A). The (C vs. B) contrast is secondary and is not considered in computing power.

The required sample size for the study was powered for testing 2 primary contrasts of change in IGF-1 over time in (1) lifestyle (arm B) vs. self-directed comparison (arm A), and (2) metformin (arm C) vs. self-directed comparison (arm A), each with 80% power and a 2-sided z test with alpha of 0.025. Assuming common SD at baseline and 6-month visit of 60 ng/ml,⁵¹ and a correlation of 0.90 between IGF-1 measures at baseline and 6-month⁴⁷, a total sample of 120 individuals (i.e. N=40 per arm) will allow the detection of a difference of 17.4 ng/ml (~10% reduction) or greater in change of IGF-1 over time between an active intervention arm and the control arm. With 20% random attrition, this trial will still be able to detect a difference

of 19.4 ng/ml or greater in change of IGF-1 over time between an active intervention arm and the control arm.

With the same sample size, the minimal detectable between arm difference in change of IGF1:IGFBP3 ratio over time were evaluated in a similar fashion for (1) arm B vs. A, and (2) arm C vs. A, each with 80% power and a 2-sided alpha of 0.025. Assuming common SD at baseline and 6-month visit of 11 using data available from the POWER trial,⁸¹ and a correlation of 0.80 between IGF-1:IGFBP3 ratio at baseline and 6-month⁴⁷, a total sample of 120 individuals (i.e. N=40 per arm) will allow the detection of a difference of 5.01 (~15% reduction) or greater in the change of IGF-1:IGFBP3 ratio over time between an active intervention arm and the control arm. With 20% random attrition, this trial will still be able to detect a difference of 5.67 or greater in change of IGF-1:IGFBP3 ratio over time between an active intervention arm and the control arm. We will explore the difference in outcome changes over time between arm B and C but this trial is not powered for this test, as the difference between these 2 arms may be small.

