A cross-sectional analyses among 700 breast cancer patients indicated higher physical activity levels were associated with lower IGF-I and IGF-3 levels.³⁷ Clinical trials have also demonstrated that exercise programs among breast cancer patients result in lower IGF levels.^{38,39} It was suggested that the strongest association among physical activity and IGF levels among breast cancer patients was associated with higher BMI, lower baseline physical activity levels and the absence of tamoxifen therapy.³⁸ However many of the extant trials have focused on exercise programs that were independent of weight loss efforts. It is not clear if aerobic exercise recommendations associated with a weight loss also result in decreases of IGF levels. Moreover the association among physical activity and IGF appears strongest among breast cancer survivors. No association was found between physical activity and IGF among prostate cancer survivors in three different trials.³⁸

There is some evidence that the type of diet can influence IGF-1 levels. A high-protein diet has been shown to increase IGF-1 among men with prostate cancer,⁴⁰ men with type II diabetes,⁴¹ and among middle-aged non-obese persons.⁴² Reduction in calories, however, has not been noted to lead to decreased IGF-1 levels,^{35,42,43} except when weight loss was substantial.³⁴

Among healthy adults, IGF-1 measurements have been shown to be stable over time.⁴⁴⁻⁴⁷ For example, In a study of over 800 older adults, a correlation of $r=0.94$ was found for IGF-1 levels measured by Immunoradiometric assay 8-54 days apart.⁴⁴ In a study of 1000 Brazilian adults 21-70, IGF-1 levels measured 12 weeks apart had a correlation of $r=0.91$, and the variation between the two measurements was 20% or less in 99% of people.⁴⁷ Regardless of body mass index, IGF-1 and IGFBP-3 were stable throughout a 24-hour observation period in both normal weight and overweight and obese participants.⁴⁸ IGF-1 has also been demonstrated to be stable in cancer patients, both throughout the day⁴⁹ and across several months.⁵⁰⁻⁵²

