4. OVERVIEW OF TRIAL DESIGN

This is a prospective, single-center randomized trial with three arms, and an allocation ratio of 1:1:1. The study design is an efficacy study to evaluate the effect of metformin and coachdirected behavioral weight loss versus self-directed weight loss on IGF-1 and IGF-1 to THE IGFBP-III ratio blood levels after 6 and 12 months of intervention. The coach-directed Behavioral Weight Loss arm is a web-based remote delivery and communication system that promotes healthy behavioral changes. The Metformin arm is a pharmaceutical intervention of oral metformin. This is a secondary prevention study for men and women who have survived solid malignant tumors.

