17.2 General Statistical Approach

The primary endpoint of this trial is the 6-month change in level of IGF-1 and IGF1 to IGFBP-III ratio among the Coach-Directed Behavioral Weight Loss arm versus self-direct arm (B vs. A), and metformin arm compared to self-direct arm (C vs. A). Intervention effects will be analyzed using intent-to-treat. Each active intervention arm will be compared with the control arm using

likelihood based mixed effects linear regression models utilizing data from all 3 time points, i.e. baseline, 6, and 12 months, simultaneously, as following.

The primary analysis model: The mean model for the mixed effects regression will be structured to include 2 binary intervention arm indicators (for Group B and C), 3 binary followup time indicators (for 3-, 6- and 12-month follow-up), and the cross-product interaction terms between the group and time indicators (6 interaction terms), and the covariance model will employ a 4x4 unstructured covariance matrix to allow different outcome variances and account for the intra-individual outcome correlations over time. Race and baseline BMI levels, the variables used for stratifying the randomization, will be included in the mean model. Other variables found not to be balanced between the trial arms will also be included as necessary. Outcomes may be transformed as needed to satisfy the distributional assumptions for the likelihood approach.

The primary testing contrasts of this trial will be the 2 aforementioned pairwise comparisons at 6 months, which will be evaluated through the regression coefficients of the Group B by 6month interaction term (B vs. A), and Group C by 6-month interaction term (C vs. A), respectively. The secondary testing contrasts include B vs. C of change in outcomes at 6month, and the 3 pairwise group comparisons of outcome changes at 12 months, which will be evaluated using the same model through the corresponding group by time interaction terms.

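### The only stated test level is a flat 0.025 per primary contrast; a step-down rule within each outcome keeps the 5% bound and gains up to about 5 points of power, if both arms work

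*Combined protocol and SAP*

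**What the plan says.** Section 16 (Sample Size) makes B vs A and C vs A the primary contrasts and sets the third comparison aside: "The (C vs. B) contrast is secondary and is not considered in computing power". It powers the two primary contrasts for IGF-1, "each with 80% power and a 2-sided z test with alpha of 0.025", and uses the same two-sided 0.025 for the IGF-1:IGFBP3 ratio. The text does not name a multiplicity method, but 0.025 for each of two contrasts is an equal split of 5%.

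Section 17.2 (General Statistical Approach) says "The primary testing contrasts of this trial will be the 2 aforementioned pairwise comparisons at 6 months", each read from its group-by-6-month coefficient in the mixed model. It gives no significance level, no multiplicity procedure and no order of testing. Section 4 specifies "an allocation ratio of 1:1:1", and arm A is the comparator in both contrasts.

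**The concern.** If the 0.025 from the sample-size section is carried into the analysis unchanged, each contrast is judged without regard to the other. Suppose one intervention gives p = 0.01 and the other p = 0.03. The flat rule does not reject the second. Holm does, with the familywise error for that outcome still held at 5%.

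The stake is power that the trial cannot easily obtain otherwise. Section 16 ties the enrolment of about 120 to available resources, and primary Aims 1 and 2 hypothesise an effect in both active arms, which is the situation in which a step-down rule helps most.

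**Working it through.** **Inputs (Section 16 unless noted).** IGF-1 SD 60 ng/ml at both visits; baseline to 6-month correlation 0.90; 40 per arm (32 after 20% attrition); two-sided alpha 0.025; stated detectable difference 17.4 ng/ml (19.4 after attrition). Allocation is 1:1:1 (Section 4).

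**1. The plan's own figure.**
- SD of change = 60 × √(2 × (1 − 0.90)) = 26.83.
- SE of a contrast = 26.83 × √(2/40) = 6.00.
- Detectable difference at 80% power = (2.241 + 0.842) × 6.00 = 18.5 ng/ml, against 17.4 stated.
- Power at 17.4 = Φ(17.4/6.00 − 2.241) = Φ(0.659) = 74.5%.

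The stated 17.4 therefore does not follow from the stated inputs. That is a separate matter. Results are given at both values, and the gain is about the same at each.

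**2. Correlation of the two statistics.** With equal arms and a common variance, each contrast has variance 2σ²/n and the two share the arm A term, so their covariance is σ²/n and their correlation is 0.5.

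**3. Critical values and error, both nulls true, one outcome.**

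| Rule | Larger statistic against | Other against | Familywise error |
|---|---|---|---|
| Flat 0.025 | 2.241 | 2.241 | 4.65% |
| Single-step Dunnett | 2.212 | 2.212 | 5.0% |
| Holm | 2.241 | 1.960 | 4.65% |
| Step-down Dunnett | 2.212 | 1.960 | 5.0% |

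**4. Where the gain arises.** Holm power for contrast 1 = P(|Z₁| > 2.241) + P(1.960 < |Z₁| ≤ 2.241 and |Z₂| > 2.241). At 17.4 ng/ml the first term is 74.5%. The band from 1.960 to 2.241 holds Φ(0.940) − Φ(0.659) = 82.6% − 74.5% = 8.1%. If both arms have the effect, the other contrast is also rejected in about 5.0 of those 8.1 points, which gives 79.5%. If the other arm has no effect, it is rejected in only about 0.2 of them.

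**5. Power, from the bivariate normal with correlation 0.5.**

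| True effects | Flat | Single-step Dunnett | Holm | Step-down Dunnett |
|---|---|---|---|---|
| Both arms 17.4, per contrast | 74.5% | 75.4% | 79.5% | 80.0% |
| Both arms 17.4, both rejected | 61.4% | 62.6% | 71.4% | 71.6% |
| Both arms 18.5, per contrast | 80.0% | 80.8% | 84.6% | 84.9% |
| Both arms 18.5, both rejected | 68.7% | 69.8% | 77.8% | 78.0% |
| 17.4 in one arm, none in the other | 74.5% | 75.4% | 74.6% | 75.6% |
| 32 per arm, both 19.4, per contrast | 74.2% | 75.2% | 79.3% | 79.7% |

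For the ratio (SD 11, correlation 0.80, SE = 11 × √0.40 × √(2/40) = 1.556) at the stated 5.01 in both arms, power per contrast goes from 83.6% (flat) to about 87.7% (Holm) or 88.0% (step-down Dunnett).

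Using the shared control alone (the single-step Dunnett column) adds 0.8 to 0.9 point. The rest comes from stepping down.

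**The case against.** The strongest reply is that nothing here is wrong. A flat 0.025 is a valid split, it has simple matching 97.5% intervals, and choosing Holm or step-down Dunnett is a choice between valid procedures. That stands, and it is why this is an improvement and not an error.

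Four stronger readings are tempting, and the documents do not support them.

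- **That the plan will call a contrast negative when p lies between 0.025 and 0.05.** A reader might infer this, but 0.025 appears only in the sample-size section. Section 17.2 sets no level, and sizing at 0.025 does not rule out Holm at analysis.
- **That the gain is 5 points in general.** It needs both arms to have the design effect. Section 3.4 calls the relation of weight loss to IGF-1 unclear and cites studies with no change or an increase, while Section 3.8 reports human reductions with metformin. Section 16 allows that the B–C difference may be small. Equal effects are one scenario among several.
- **That the loss comes mainly from ignoring the shared control.** That accounts for less than 1 point.
- **That error for the trial stays at 5%.** The bound is per outcome. With two primary outcomes there are four primary tests. Assuming a between-outcome correlation of 0 to 0.9 (not given in the documents), the chance of any false positive is about 9.1% to 6.6% with 0.025 each, and 9.7% to 7.1% with step-down Dunnett in each outcome.

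There is also a modest price inside the 5% bound. If one arm works at 17.4 and the other does nothing, the chance of wrongly rejecting the null contrast rises from 2.5% to about 4.1% with Holm.

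**Conclusion.** The point holds as a low-cost gain in efficiency. Holm rejects everything the flat split rejects and sometimes more, within the same 5% bound for each outcome, so it is never less powerful. The gain per contrast at 17.4 ng/ml is about 5 points if both arms have that effect. It is 0.2 point (Holm) to about 1 point (step-down Dunnett) if only one does. Power to establish both interventions rises by about 10 points in the first case.

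The figures assume the plan's SD and correlation, a z test, equal arms and a common variance. The correlation of 0.5, and with it the Dunnett value 2.212, shifts if attrition or variances differ by arm. Holm's error control does not depend on that correlation. How error is shared between IGF-1 and the ratio is a separate question that this change does not answer.

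**What to change.** Add one paragraph to Section 17.2, fixed before any outcome comparison by arm is seen:

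- Within each primary outcome, B vs A and C vs A at 6 months are tested by Holm at two-sided 5%: the smaller p-value against 0.025 and, if that is rejected, the other against 0.05.
- Step-down Dunnett is an alternative: the larger absolute statistic against 2.21, then the other against 1.96, using t-based equivalents. It gains up to about 1 point over Holm but relies on the correlation between the contrasts.
- The same rule applies at whatever overall level each primary outcome is allotted, with 0.025 and 0.05 scaled accordingly.
- Report simultaneous intervals (2.24 × SE to go with Holm, 2.21 × SE to go with Dunnett) and state that the step-down test governs the decision.

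The cost is that paragraph. No participants, visits or assays are added. The small downside is that a simultaneous interval may include zero for a contrast that the step-down test rejects in a borderline case, which the last item deals with in advance.

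### The stated IGF-1 detectable differences (17.4 and 19.4 ng/ml) do not follow from the plan's own inputs, which give 18.5 and 20.7; power at the stated differences is about 74%, not 80%.

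*Combined protocol and SAP*

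**What the plan says.** Section 16 fixes the total at about 120 participants because that is what resources allow. It then reports the smallest between-arm difference in change that each of the two primary contrasts (coach-directed vs. self-directed, metformin vs. self-directed) can detect.

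- **Test and error rates:** "each with 80% power and a 2-sided z test with alpha of 0.025".
- **Variability of IGF-1:** "Assuming common SD at baseline and 6-month visit of 60 ng/ml".
- **Correlation of IGF-1:** "a correlation of 0.90 between IGF-1 measures at baseline and 6-month".
- **Size:** 40 per arm. Section 4 confirms "an allocation ratio of 1:1:1".
- **Result for IGF-1:** the design "will allow the detection of a difference of 17.4 ng/ml (~10% reduction) or greater in change of IGF-1 over time". With 20% random attrition the plan claims detection "of 19.4 ng/ml or greater in change of IGF-1 over time between an active intervention arm and the control arm".
- **Result for the ratio:** with SD 11, correlation 0.80 and the same alpha and power, the design "will allow the detection of a difference of 5.01 (~15% reduction) or greater". After 20% attrition the figure is 5.67.

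No other adjustment or formula is given. Section 17.2 tests the same quantity, using the group-by-6-month interaction terms of the mixed model.

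**The concern.** Because the sample size was not derived from a target effect, the detectable difference is the only result of the power calculation, and it should follow from the inputs beside it. For IGF-1 it does not, and the error makes the trial look more sensitive than it is. A true difference of 17.4 ng/ml would be missed about 25.5% of the time rather than 20%. A reader of a null IGF-1 result would take from section 16 that an effect of about 10% had been sought with 80% power. The ratio figures miss in the other direction, so the section as a whole cannot be taken as the output of its stated assumptions.

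**Working it through.** **Inputs (all from section 16).** IGF-1: SD 60 ng/ml at both visits, r = 0.90. Ratio: SD 11, r = 0.80. n = 40 per arm, or 0.8 × 40 = 32 after attrition. Two-sided alpha 0.025, so z = 2.2414. Power 80%, so z = 0.8416. The multiplier is 2.2414 + 0.8416 = 3.083.

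**Formulas.**
- SD of change = SD × √(2(1 − r))
- SE of the difference in mean change = SD of change × √(2/n)
- Detectable difference = 3.083 × SE
- Power at a stated difference = Φ(difference/SE − 2.2414)

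**IGF-1.** SD of change = 60 × √0.20 = 26.83 ng/ml.
- n = 40: SE = 26.83 × √(2/40) = 6.00. Detectable difference = 3.083 × 6.00 = 18.50, against the stated 17.4. Power at 17.4 = Φ(2.900 − 2.2414) = 74.5%.
- n = 32: SE = 26.83 × √(2/32) = 6.71. Detectable difference = 20.68, against the stated 19.4. Power at 19.4 = Φ(2.892 − 2.2414) = 74.2%.
- Sample size for 80% power at 17.4: 2 × 26.83² × 3.083² / 17.4² = 45.2, so 46 evaluable per arm.

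**Ratio.** SD of change = 11 × √0.40 = 6.957.
- n = 40: SE = 1.556. Detectable difference = 4.80, against the stated 5.01. Power at 5.01 = 83.6%.
- n = 32: SE = 1.739. Detectable difference = 5.36, against the stated 5.67. Power at 5.67 = 84.6%.

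**Could another standard method give 17.4 and 19.4?** Keeping SD 60, r 0.90 and 80% power:

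| Method | n = 40 | n = 32 |
|---|---|---|
| Stated in the plan | 17.4 | 19.4 |
| Change score, z, two-sided 0.025 (as described) | 18.50 | 20.68 |
| Change score, t, two-sided 0.025 | 18.80 | 21.11 |
| ANCOVA variance, z, two-sided 0.025 | 18.03 | 20.16 |
| ANCOVA variance, t, two-sided 0.025 | 18.33 | 20.58 |
| Change score, z, two-sided 0.05 | 16.81 | 18.79 |
| Change score, t, two-sided 0.05 | 17.02 | 19.09 |

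The most favourable method at the stated alpha (ANCOVA variance with z) still gives only 76.9% and 76.6% power at the stated differences. A wider search over alpha, power, correlation and sample size found one combination that keeps SD 60, r 0.90, 40 and 32 per arm and 80% power and matches both IGF-1 figures after rounding: ANCOVA variance with a one-sided alpha of 0.0167 (17.37 and 19.42). That contradicts the stated alpha, the stated sidedness and the change-score contrast. It also fails for the ratio: 11 × √(1 − 0.80²) = 6.60, and (2.128 + 0.8416) × 6.60 × √(2/40) = 4.38, not 5.01.

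**What the stated figures would need.** Holding the rest fixed, 17.4 requires a correlation of about 0.912 or an SD of about 56.4. The figure 5.01 requires a correlation of about 0.782 or an SD of about 11.5.

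**Do the two outcomes share one explanation?** The IGF-1 figures are about 6% too small (17.4/18.50 = 0.941). The ratio figures are about 4% to 6% too large (5.01/4.80 = 1.044; 5.67/5.36 = 1.058). A change of alpha, power or sample size common to both would move both in the same direction, so it cannot repair both.

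**Attrition step.** Under the z test, going from 40 to 32 per arm multiplies the detectable difference by √(40/32) = 1.118. For IGF-1 the stated step is 19.4/17.4 = 1.115, which is within rounding (19.35/17.45 = 1.109 to 19.45/17.35 = 1.121). For the ratio it is 5.67/5.01 = 1.132, which is outside rounding (5.665/5.015 = 1.130 to 5.675/5.005 = 1.134). No single SD and correlation therefore gives both ratio figures.

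**The case against.** The best defence is that 0.90 is a rounded input. Section 16 cites a study of Brazilian adults for the correlation, and section 3.4 reports that study's figure as 0.91. With r = 0.91 the same formula gives 17.55 and 19.62 ng/ml, and power at the stated differences is 79.3% and 79.0%. With r = 0.912, which rounds to 0.91, it gives 17.35 and 19.40, matching both stated figures to rounding. On that reading the IGF-1 claim is nearly right and only the printed correlation is wrong.

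This is a plausible account of how the figures arose, and the sponsor should be asked about it. It does not make the section correct. The 0.91 is a 12-week correlation, and the plan chose 0.90 for the 6-month interval. At 0.91 exactly, neither figure reproduces. Nor does it touch the ratio figures.

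Three further objections are partly right:
- The IGF-1 attrition step is consistent within rounding. Only the ratio step fails.
- Opposite errors in the two outcomes do not by themselves show that the IGF-1 figures are wrong, since each outcome has its own SD and correlation. The direct recalculation shows it.
- The practical effect is limited. The sample size was set by resources, the gap is 1.1 ng/ml at 40 per arm, and a null result should be read from its confidence interval. If about 10% corresponds to 17.4 ng/ml, the implied baseline mean is 174 ng/ml (not stated in the plan), and the recomputed 18.5 is 10.6% of it. That bounds the harm but does not justify a power statement that is wrong as written.

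**Conclusion.** The concern holds. On the inputs printed in section 16, the detectable IGF-1 differences are understated by 1.1 and 1.3 ng/ml, and power at the stated values falls 5 to 6 points short of 80%, for both primary contrasts and in the attrition scenario. The ratio figures are also wrong but conservative, with power of about 84% to 85%.

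The conclusion takes the SD, correlation, alpha and 40 per arm as printed, complete-case attrition to 32 per arm, and a change-score contrast, which is what the interaction term in section 17.2 estimates when data are complete. It would weaken for IGF-1 only if the sponsor shows that a different correlation or SD was used. The error does not bias the treatment estimate or affect the analysis model.

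**What to change.** Ask the sponsor which SD, correlation, test and variance formula produced the four figures, and in particular whether a correlation near 0.91 was used for IGF-1. Then correct section 16 in one of three ways:

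1. Keep the printed inputs and state detectable differences of 18.5 ng/ml (40 per arm) and 20.7 ng/ml (32 per arm) for IGF-1, and 4.80 and 5.36 for the ratio.
2. Keep the printed differences and state their power: about 74% for IGF-1, and about 84% (40 per arm) and 85% (32 per arm) for the ratio.
3. Replace the inputs or method with those actually used, justify them for a 6-month interval, and confirm that all four figures reproduce.

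The approximate percentage reductions should be rechecked at the same time, with the baseline means they refer to. The cost is a wording change in section 16 and a slightly less favourable IGF-1 statement under the first two options. Sample size, endpoints, alpha and analysis stay as they are.
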